remain blinded to study drug treatment assignment during the blinded treatment period in Study Period A as well as during the Study Period B (see Section 3.8 for details on blinding). Following the *data snapshot date* for the Study Period A *primary readout*, selected members of the Sponsor team may become unblinded for the purpose of analysis and interpretation of Study Period A data. *During Study Period B, after the results of Study Period A are available, study participants may choose to learn their mutation carrier status (see Sections 3.8 and 3.9 for additional information).*

Participants will have the option to receive the same dose (720 mg SC Q2W or 60 mg/kg IV Q4W) they were receiving at the end of the Study GN28352 *Period A* or switch to the higher dose of 60 mg/kg IV Q4W if they have not already switched. See Section 3.2.2 for rationale for crenezumab dosage.

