4.10.8 Determination of Sample Size

This study will enroll up to 300 participants: up to 200 participants will be enrolled in the carrier cohort and up to 100 participants will be enrolled in the non-carrier cohort.

Participants in the carrier cohort will be randomized in a 1:1 randomization ratio of active to placebo participants. The study was originally powered to compare the mean change from baseline over 260 weeks in the API ADAD Composite Cognitive Test total score between the crenezumab group and the placebo. Assuming a 25% dropout rate, two-sided testing at an overall 0.05 level, a placebo group CV of 65% for the Week 260 change scores ($=100\% \times$ standard deviation of placebo participant change scores/mean of placebo participant change scores) and 100 participants per arm, the study will have at least 80% power to detect a true effect of 30% reduction of the mean decline in the placebo group.

Participants in the non-carrier cohort will all receive placebo and will be included in the study in order to maintain the genotype blind.

The study was originally powered based on the API ADAD Composite Cognitive Test Battery total score. However, due to concerns about learning effects and general lack of sensitivity to change in a cognitively normal population, before study unblinding, the Sponsor performed a blinded power analysis on the original primary endpoint API ADAD Composite Cognitive Test Battery Total Score and the secondary clinical endpoints. The Sponsor decided to promote the FCSRT Cueing Index from a secondary endpoint to part of a primary endpoint family (along with the API ADAD Composite) due to its favorable statistical properties and clinical relevance as a sensitive measure of episodic memory dysfunction—the hallmark of emerging symptomatic AD and the most commonly observed, early, and consistent neuropsychological marker of AD (Tounsi et al. 1999; Bateman et al. 2012; Caselli et al. 2020) In the SAP, the Sponsor will provide details of the blinded power analysis along with the evidence of type I error control.

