To understand the treatment effect on each component of one of the primary endpoints (API ADAD Composite Cognitive Test total score), the same primary analysis model will be run on each component. The 95% CIs and p-values for the treatment effect estimator will be presented. A forest plot will be made.
- To explore whether decline accelerates or decelerates, a quadratic RCRM where leading t^2 terms (treatment and time 2 interaction terms and random quadratic term) are added to the primary analysis model. The covariance matrix of $\{u_{0i}, u_{1i}, u_{2i}\}$ is assumed to be unstructured and all random effect terms are assumed to be independent of the pure error term. Specifically, this model is written as:

$$Y_{ij} = \alpha + (\text{Randomization Factors})_i + u_{0i} + (\beta + \beta_x I_{x,i} + u_{1i})t_{ij} + (\theta + \theta_x I_{x,i} + u_{2i})t_{ij}^2 + \epsilon_{ij}.$$

All statistical inferences as in the primary analysis model along with the point estimates of θ_x and 95% CI will be presented.

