5.10.1.1 Delayed-Start Analyses

The delayed-start analysis will be used for all continuous efficacy endpoints that will be collected in Study Period B and the potential OLE study. Since the potential OLE will not be published by the finalization of this SAP, the description in this section is in general terms and does not focus on any specific endpoint. However, statistical testing will be performed only on the API ADAD Composite Cognitive Test total score and the FCSRT Cueing Index. Other continuous efficacy endpoints, including clinical endpoints, fluid biomarkers, and imaging biomarkers, will be considered exploratory and thus, formal statistical testing will not be done.

Figure 4 illustrates the concept of the delayed-start analysis. As shown in the figure, a treatment effect is assumed in Period A of Study GN28352; the disease progression slope of mutation carriers from the Study Period A crenezumab arm is assumed to be the same in Study Period B and in the OLE; the disease progression slope of mutation carriers from the Study Period A placebo group; however, will have a different slope in Study Period B and in the OLE. The statistical model details can be found in

Appendix 3. To control the type I error within the delayed-start analyses, the fixed testing sequence is specified in the following figure. The α level in each testing is a two-sided 0.05. If at any stage the null hypothesis H_0 is not rejected, then the formal testing procedure will stop.

Figure 4 Illustration of Delayed-Start Analyses Using Data from the Beginning of Period A of Study GN28352 to the End of Study Period B or OLE

[figure not shown]
[figure not shown]

Figure 5 Testing Hierarchy for Delayed-Start Analyses

API = Alzheimer's Prevention Initiative; ADAD = autosomal-dominant Alzheimer's disease; FCSRT = Free and Cued Selective Reminding Task.

Note: For a definition of H0 and H1, please see Section 2.

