$$\lambda[c] = \frac{\left(\hat{V}(\hat{\beta}_x[c]) \right)^2}{\left(\hat{V}_{cren}^{comp} \right)^2 + \left(\hat{V}_{pbo,MAR} \right)^2}.$$

We will then perform the imputation based on $c=0$. This scenario assumes that the mean slope from the participants with missing values from the crenazumab arm is the same as the estimated overall placebo slope. We note that this assumption is already conservative in estimating the treatment effect because it implicitly assumes participants

on treatment will even do worse than an average placebo participant, after dropping out of the study.

DELAYED-START ANALYSIS MODEL FROM SECTION 5.10.1.1

The statistical model for this delayed-start analysis can be written as:

$$Y_{ij} = \alpha + (\text{Randomization Factors})_i + u_{0i} + (\beta + \beta_x I_{x,i} + u_{1i})t_{ij} + (\beta_{x,B/CAST} t_{ij} - \beta_{x,B/OLE} T_i)(1 - I_{x,i})I_{t_{ij} > T_i} + \epsilon_{ij},$$

where β_x quantifies the crenezumab annualized treatment effect in slowing down the disease progression in Period A of Study GN28352 and $\beta_{x,B/OLE}$ quantifies the treatment effect by switching from placebo to crenezumab in Period B of Study GN28352 and the OLE; T_i represents the time of the first endpoint assessment after participant i enters into Study Period B or the OLE.

Due to the common-close design of Study GN28352, mutation carriers will have varied duration of follow-up at the end Study Period of A. To calculate the crenezumab treatment effect at the end of Study Period A, we first calculate the arithmetic mean of duration in Study Period A (last endpoint assessment date – randomization date in Study Period A + 1) among mutation carriers and we call this duration \bar{T}_1 . On average, the treatment benefit in slowing down the disease progression at the end of Study Period A can be written as:

$$\Delta_1 = \beta_x \bar{T}_1.$$

Similarly, we also calculate the arithmetic average of overall duration at the end of the OLE among mutation carriers and we call this duration \bar{T}_2 . The average treatment benefit remained at the end of OLE can be written as:

$$\Delta_2 = (\beta_x - \beta_{x,B/OLE}) \bar{T}_2 + \beta_{x,B/OLE} \bar{T}_1.$$

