Note that both \bar{T}_1 and \bar{T}_2 are treated as constants and are estimated from the data. A non-inferiority test with different margins will be applied ([Liu-Seifert et al. 2015](#)). A 90% CI will be calculated for $\Delta_2 - 50\%\Delta_1$ or $\Delta_2 - 30\%\Delta_1$, depending on the specified margin in the test; if the lower limit of the CI is greater than 0, then the H_0 will be rejected, meaning that by the end of the OLE at least 50% (or 30%) of the treatment effect at the end of Study Period A is preserved.

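### The delayed-start model lets only former-placebo carriers change slope in Period B, so a change in decline common to both arms is read as an effect of switching and biases the retained-benefit test

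*SAP*

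**What the plan says.** SAP 5.10.1.1 and Appendix 3 define a delayed-start analysis for the API ADAD composite and the FCSRT Cueing Index, triggered two years after the last Period A efficacy visit. All carriers receive crenezumab in Period B (SAP 1.2.2).

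- Early-start arm: "the disease progression slope of mutation carriers from the Study Period A crenezumab arm is assumed to be the same in Study Period B"; this extends to any OLE.
- Former-placebo arm: it "will have a different slope in Study Period B and in the OLE".
- Model: the only term that acts after Period A is multiplied by (1 - I_x), so it is zero for early-start carriers. Its coefficient "quantifies the treatment effect by switching from placebo to crenezumab in Period B of Study GN28352 and the OLE". The formula prints two subscripts for this coefficient (B/CAST and B/OLE); I read them as one parameter, beta_xB.
- Change point: T_i "represents the time of the first endpoint assessment after participant i enters into Study Period B or the OLE". In Protocol Appendices 5 and 6 the first cognitive assessment of Period B is at Week 25.
- Contrast: Delta1 = beta_x x T1 and Delta2 = (beta_x - beta_xB) x T2 + beta_xB x T1. T1 is the mean Period A duration and T2 the mean overall duration.
- Decision: a 90% CI is formed for Delta2 - 50% (or 30%) x Delta1, and "if the lower limit of the CI is greater than 0, then the H_0 will be rejected".

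For the Period A primary endpoints the SAP does allow for non-linear decline. Section 5.3.4 plans an MMRM to relax linearity. Section 5.3.5 adds a further model: "To explore whether decline accelerates or decelerates, a quadratic RCRM". Nothing comparable is attached to the delayed-start test.

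**The concern.** Once every carrier is on crenezumab, the early-start arm shows what happens to decline over time for reasons other than switching. The model does not use it that way. If decline steepens in both arms, two things follow. The steepening among former-placebo carriers is booked as a poor response to switching, so beta_xB is too low and Delta2 too high. The steepening among early-start carriers is averaged into one straight line, so beta_x and Delta1 are too low. Both errors ease the criterion. If decline slows in both arms, both errors reverse and the test becomes too strict.

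Non-linearity cannot be set aside here. Carriers enter without MCI or dementia, are expected to progress, and are followed for 5 to about 8 years in Period A plus about two more. Early-start carriers may also have a reason of their own to change slope: under Protocol 3.2.1, participants entering Period B may "switch to the higher dose of 60 mg/kg IV Q4W if they have not already switched".

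At stake is the long-term analysis that has a prespecified, alpha-controlled test sequence.

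**Working it through.** **Inputs from the documents.** 84 carriers per arm (SAP Appendix 2 simulation); 30% relative reduction and 65% placebo CV of the five-year change (SAP 3); Period A of 5 to 8 years (SAP 1.2.1, 5.3.4), taken as uniform, so T1 = 6.5; two years of Period B (SAP 5.10.1), so T2 = 8.5.

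**Assumed, because the documents are silent.** Placebo slope -1 per year; random-intercept SD 3, random-slope SD 0.5, residual SD 1.5; visits about every half year; acceleration from 0 to 100%, equal in both arms and starting at Period B entry. The SDs match the plan's CV: sqrt(25 x 0.25 + 2 x 2.25) = 3.28, and 3.28/5 = 66%.

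**The plan's own figures.** With 100 per arm less 25% dropout, 75 per arm and a standardised effect of 0.30/0.65 give 80.7% power, as stated (at least 80%). For the delayed-start test the SAP gives no operating characteristic. A lower 90% limit implies a 5% pass rate at the boundary. (Section 5.10.1.1 calls the level two-sided 0.05, which is a separate mismatch.) The Delta2 formula is algebraically correct under the SAP's own model: the arm difference at T2 is beta_x x T2 - beta_xB x (T2 - T1).

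**Boundary case.** beta_x = 0.30, so Delta1 = 0.30 x 6.5 = 1.95. True 50% retention means Delta2 = 0.975, hence beta_xB = (0.30 x 8.5 - 0.975)/2 = 0.7875. The contrast is 0.30 x (8.5 - 3.25) - 0.7875 x 2 = 0.

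**Fitting the SAP model by generalised least squares, change point at the end of Period A, 50% acceleration.** The common slope change is -0.5.

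- beta_xB falls from 0.7875 to 0.290, so 99% of the common change is charged to former-placebo carriers.
- beta_x falls from 0.300 to 0.224.
- Contrast = 0.224 x 5.25 - 0.290 x 2 = 0.60, with SE 0.434.
- Pass rate = Phi(0.597/0.434 - 1.645) = Phi(-0.27), about 40%.
- Estimated retention is 1.33/1.46 = 91%; the truth is 50%.

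**Pass rates at true 50% retention (nominal 5%)**

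| Common acceleration | Change point at end of Period A | T_i at first Period B assessment, as written |
|---|---|---|
| 0% | 5% | 0.2% |
| 25% | 17% | 4% |
| 50% | 40% | 23% |
| 100% | 87% | 91% |

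Entries shift by about a point with the visit layout. The second column is lower at small accelerations because of a separate mismatch. T_i lies about half a year after entry while T1 stops at the end of Period A. If catch-up starts at entry, the model then overstates catch-up: with linear decline it estimates 21% retention when the truth is 50%.

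**Checks, change point at the end of Period A.**

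- REML simulation at 50% acceleration: 36% (250 runs); 38% among runs with a significant Period A result.
- 30% margin at its own boundary: 12%, 25% and 62% at 25, 50 and 100% acceleration.
- Random-slope SD from 60% down to 15% of annual placebo decline, CV held at 65%, 50% acceleration: 34% to 81%.
- Smooth quadratic decline: 36% or 49%, depending on the curvature assumed.
- Deceleration of 25%: about 1%.
- No benefit truly retained: 0.6% at 50% acceleration, 13% at 100%.

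**The case against.** The strongest reply is that the model as printed is not the one with the worst error rates. With T_i at the first Period B assessment, the test is conservative until common acceleration exceeds roughly 25-30%. That stands. A reader might infer that any acceleration makes the test pass too often; the specification does not support this.

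A reader might also take the documents to show that decline accelerates. They do not. Protocol 4.10.8 mentions learning effects and a "general lack of sensitivity to change in a cognitively normal population", which concerns the composite as a measure, not the shape of decline. The quadratic model in SAP 5.3.5 is neutral on direction. The option to move to IV is open to all participants and does not fix the direction either.

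Nor do the documents support reading a pass as a claim of disease modification. Appendix 3 claims only that 50% (or 30%) of the Period A effect is preserved, and false passes stay rare when nothing is retained unless acceleration is large.

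The consequences are limited too. Period B analyses are exploratory if the study is terminated on Period A results (SAP 5.10, Protocol 4.10). The sequence is separate from the primary and key secondary testing. The RPSFT analyses also give p-values on long-term data. The Period A MMRM would show curvature about two years before this analysis is triggered. Figures 4 and 5 are not in the text available to me, so gates ahead of the retention test could not be assessed.

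These points limit the size and the severity. They do not remove the defect: the error rate depends on a constant-slope assumption that the concurrent early-start arm could replace, and the MMRM does not correct this model.

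**Conclusion.** The point holds as a structural bias whose direction is known once the direction of the common change is known, and whose size is not. Acceleration common to both arms inflates the pass rate relative to no acceleration under either reading of T_i; deceleration lowers it. Whether the rate exceeds 5% depends on T_i. With the change point at the end of Period A, any acceleration does it. As literally written, it takes roughly 25-30%, because the T_i mismatch pulls the other way. Two biases that offset each other at one unknown rate of acceleration are not a reason to keep both.

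The figures rest on an assumed acceleration, an assumed split of variance, catch-up starting at Period B entry and two years of Period B. This should be fixed, but it does not threaten the trial's primary conclusions.

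**What to change.** Make both changes in SAP Appendix 3:

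1. Add a Period B slope-change term common to both arms, gamma x (t - T_i) x I(t > T_i), and delete from 5.10.1.1 the assumption that the early-start slope is unchanged. beta_xB then measures the former-placebo change relative to the concurrent early-start arm, whatever the reason that arm's slope moves.
2. Set T_i at the end of Period A (entry into Period B), so that it matches T1 in Delta1 and Delta2.

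The Delta1 and Delta2 formulas and the testing order stay as they are, because gamma cancels from the arm difference.

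Both parts are needed. The first alone, with T_i as written, gives a pass rate of about 0.3% and 21% estimated retention when the truth is 50%. Together they give 5% at the boundary at every acceleration tried.

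The cost is one parameter. The SE of the contrast rises about 3-5% (0.434 to 0.447 in this set-up). Power under full retention and linear decline goes from about 73% to 70%, compared with the SAP model using the aligned change point. Compared with T_i as literally written, where it is about 52-53%, power improves.

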5.10.1.2 Rank-Preserving Structural Failure Time Analyses

The RPSFT analysis will be used for the 2 time-to-event (TTE) endpoints below, also collected in Period B of Study GN28352 and the OLE. The TTE endpoints will anchor the randomization date from Period A of Study GN28352 as the reference date.

- Time to progression to non-zero in CDR global score
- Time to progression from preclinical AD to MCI due to AD or from preclinical AD to dementia due to AD

The Sponsor will ensure that the TTE endpoints will remain as objective/unbiased as possible in Period B of Study GN28352 and the OLE. *During* Period B of Study GN28352, the Sponsor will be unblinded to the mutation status and treatment assignment when analyzing the Study Period A results. *However*, participants, contract research organization staff, and blinded site staff will remain blinded *to treatment allocation in Study Period A*. Furthermore, an independent adjudication committee will still be in place to adjudicate cases deemed by the site that have progressed from preclinical AD to MCI due to AD or from preclinical AD to dementia due to AD. If the Sponsor initiates the OLE after the results of Study GN28352 are available, we anticipate that *only mutation carriers will be eligible for the OLE*.

The RPSFT method as introduced by Robins and Tsiatis (1991) provides an estimate of the overall event time for participants randomized into placebo group in Study Period A had treatment switching not occurred. With this model, we assume that the crenezumab treatment effect on event time is the same regardless of when crenezumab is given. It estimates overall event time measured from the time of treatment switching by applying an estimate of the benefit of crenezumab (derived iteratively and referred to as the inverse of the acceleration factor). The treatment switching does not happen for participants randomized into the crenezumab group in Study Period A; therefore, their event time can be directly used. The stratified log rank test, where the stratification factors are from Study Period A, will then be used to calculate the two-sided p-value; the HR for recurrence will be estimated using a stratified Cox proportional hazards model, and the 95% CI for the HR will be provided. Some stratification factor(s) may be removed from the stratified analyses if there is risk of non-convergence or sparse strata.

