The common-close design will increase the power of detecting a difference between crenezumab and placebo by utilizing the data obtained from each participant, including those data from participants with more than 5 years' treatment duration, in the overall analysis. Furthermore, the common-close design allows similar duration of treatment with the higher IV dose (60 mg/kg IV) or matching placebo, for analysis of treatment at a higher dose.

The rationale for changing the study design is to maintain statistical power of 80% to detect a treatment effect (see Section 4.10 for further details)—despite the fact that only 252 participants of the 300 originally planned could be recruited from this kindred—and to allow reasonable duration of treatment for assessment of benefit at the higher dose.

Study Period A will be continued until the last ongoing enrolled participant has reached 260 weeks, as far as is practical (see Section 4.5.4).

One or more interim analyses may be conducted at the Sponsor's discretion at any point during the study. Such an analysis may be triggered by, for example, the availability of results from another clinical study with crenezumab.

3.2.1

Rationale for Study Period B

For the first participants reaching the final efficacy visit in Study Period A (End of Treatment-A or End of Treatment-B visit), several months will pass before results from Study Period A are available *and a longer period of time until regulatory approval or a mechanism of post-trial access is set up*. To honor the long commitment of participants and not to force a treatment gap in the case crenezumab is effective in slowing disease progression, participants will be offered the opportunity to continue to receive blinded study drug until *regulatory approval or post-trial drug access is started* (via an OLE or other program) or there is a decision to terminate the development of crenezumab on the basis of the results in Study GN28352. *Data collected in Study Period B will be used to assess the long term safety and efficacy of crenezumab.* Continuation into Study Period B is optional.

Treatment and Dosing

After completing the final efficacy visit in Study Period A, all mutation carriers who enter Study Period B will receive crenezumab and all non-carriers entering Study Period B will continue to receive placebo. Participants, site staff, vendor staff, and Sponsor will

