4.10.10 Analyses for Study Period B

All efficacy analyses will include data from Study Period A and Study Period B. The analysis population will be based on mITT population. The delayed-start efficacy analyses and rank-preserving structural failure time analyses will be triggered 2 years after the last efficacy visit in Study Period A.

All the safety analyses described in Section 4.10.4 will be reported.

Summaries of conduct of study and summaries of treatment group comparability/demographics and baseline characteristics will also be presented. The population is based on the Study Period B ITT population. The analyses are similar to what are specified for Study Period A and are specified in the SAP.

Pharmacokinetic and PD analyses will be handled in a similar fashion to Study Period A.

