5.10 ANALYSES FOR PERIOD B AND OPEN-LABEL EXTENSION STUDY

This section will pre-specify the main analyses planned for Study Period B of this study and the potential OLE study.

If the Sponsor decides to terminate the study based on the primary analysis results from Study Period A, all the data and analyses from Study Period B will be considered as exploratory in nature; a final CSR will be written, including these extra data. However, if the Sponsor decides to extend Study Period B or initiate an OLE study, a planned data snapshot will occur 2 years after finished the last efficacy visit in Study Period A.

Three analysis populations are defined for this snapshot:

- Study Period A mITT population: the mITT population defined in Section 4: all randomized participants who received at least 1 dose of study drug; participants are grouped according to the treatment assignment at randomization; all efficacy analyses in this snapshot are based on mITT population among the mutation carriers
- Study Period B safety population: all randomized participants that received at least 1 dose of study drug in Study Period B; participants are grouped according to the actual treatment received; participants on placebo who received more than 2 doses of crenezumab will be grouped in the crenezumab arm
- OLE safety population: all OLE enrolled participants that received at least 1 dose of study drug (crenezumab)

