Next, we show through simulations *to support the proof*. For simplicity, we assume the BP analysis is performed on 2 endpoints X and Y , where the experimental drug has no treatment effect on X but *could have* a treatment effect on Y .

Mimicking study GN28352, we assume the following:

- 84 participants randomized to the placebo arm and 84 participants randomized to the experimental arm, with no dropout
- Endpoints X and Y both follow a normal distribution within each arm
- Within endpoints X and Y , without loss of generality, the standard deviation in both arms is 1
- Endpoint X has no treatment effect and the placebo arm mean is 1/0.65 (protocol CV assumption on API ADAD Composite Cognitive Test total score=0.65)

In the simulation study, we vary the following, which yields 135 scenarios:

- Treatment effect in endpoint Y in RR scale: 0%, 50%, and 100%
- Placebo mean in endpoint Y : 0, 1, 1.5, 2, 10
- *Endpoints X and Y follow a bivariate normal distribution with*
 - Correlation between endpoint X and Y within the placebo group: $\rho_{pbo}=0.1, 0.5, 0.9$
 - Correlation between endpoint X and Y within the treatment group: $\rho_{exp}=0.1, 0.5, 0.9$

The family-wise type I error in this case equals the probability of rejecting the null H_0 in endpoint X . *When there is a treatment effect in endpoint Y , the only scenario where a type I error can happen is when endpoint X is chosen by the BP analysis.* The number of iterations in the simulation study was 100,000. We summarize the simulation results on type I error (along with the probability of choosing endpoint Y *in scenarios where endpoint Y has a treatment effect*) in [Tables 1–3](#).

Table 1 Family-Wise Strong Type I Error, Assuming 0% Treatment Effect in Endpoint Y (Type I Error in the Weak Sense)

		Placebo Mean in Endpoint Y				
		0	1	1.5	2	10
$\rho_{pbo} = 0.1$	$\rho_{exp} = 0.1$	0.05090	0.04968	0.0583	0.04965	0.04862
	$\rho_{exp} = 0.5$	0.04928	0.04963	0.04995	0.05029	0.04983
	$\rho_{exp} = 0.9$	0.05042	0.04981	0.05012	0.04894	0.05068
$\rho_{pbo} = 0.5$	$\rho_{exp} = 0.1$	0.04949	0.04898	0.04953	0.04982	0.05075

		Placebo Mean in Endpoint Y				
	$\rho_{exp} = 0.5$	0.05052	0.05048	0.05014	0.04953	0.04962
	$\rho_{exp} = 0.9$	0.04913	0.05105	0.05016	0.04927	0.04969
$\rho_{pbo} = 0.9$	$\rho_{exp} = 0.1$	0.05074	0.05068	0.05055	0.04959	0.05099
	$\rho_{exp} = 0.5$	0.05010	0.05002	0.05012	0.04951	0.05088
	$\rho_{exp} = 0.9$	0.04969	0.05063	0.04900	0.05004	0.04970

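### The RPSFT p-value and HR interval treat an estimated acceleration factor as known, so the nominal 5% test rejects about 6–11% of the time under no effect

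*SAP*

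**What the plan says.** SAP 5.10.1.2 applies the RPSFT method to time to MCI or dementia due to AD and to time to a non-zero global CDR. It sets out a sequence:

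1. Placebo carriers' time after the switch is adjusted by "applying an estimate of the benefit of crenezumab (derived iteratively and referred to as the inverse of the acceleration factor".
2. Crenezumab carriers never switch, so their observed times are used unchanged.
3. The stratified log-rank test "will then be used to calculate the two-sided p-value; the HR for recurrence will be estimated using a stratified Cox proportional hazards model", and a 95% CI for the HR is reported.

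The section gives no re-censoring rule, no bootstrap, no as-randomized p-value and no test-based interval. A bootstrap is specified elsewhere, in SAP 5.3.3, for the relative reduction on the primary endpoints.

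On timing, Protocol 4.10.10 says the "rank-preserving structural failure time analyses will be triggered 2 years after the last efficacy visit in Study Period A". On status, SAP 5.10 says that if the study is terminated on the Period A results, "all the data and analyses from Study Period B will be considered as exploratory in nature". For continuous endpoints, SAP 5.10.1.1 says "statistical testing will be performed only on the API ADAD Composite Cognitive Test total score and the FCSRT Cueing Index" and labels the rest exploratory. The two time-to-event endpoints receive a p-value with no such label.

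**The concern.** A log-rank or Cox model run on adjusted times treats the adjustment factor as a known constant. Here it is an estimate from the same events.

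Suppose crenezumab does nothing. The true factor is 1, no time needs adjusting, and the as-randomized log-rank is already a valid test. If the crenezumab arm happens to look better, the estimated factor says that drug time should be shortened to recover untreated time. Placebo carriers' post-switch time is shortened accordingly and their events move earlier. The chance imbalance is thus counted twice, and the same happens in the other direction. The p-value comes out too small and the interval too narrow.

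These are the clinical progression endpoints. If Period B is extended or an open-label study follows, readers will take their p-values and intervals at face value. The re-censoring rule changes both the size and the direction of the error, so leaving it unstated matters in its own right.

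**Working it through.** **The plan's own figure.** The documents state no operating characteristic for this analysis. Their only power figure is for the original design: 100 × 0.75 = 75 per arm after dropout and a standardised effect of 0.30/0.65 = 0.46 give 80.7% power, which agrees with the stated 80%.

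**Inputs from the documents**
- 84 carriers per arm (SAP Appendix 2: "84 participants randomized to the placebo arm and 84 participants randomized to the experimental arm, with no dropout").
- Period A lasting 5 to 8 years (Protocol 3.2; SAP 5.3.4).
- 2 years of Period B (Protocol 4.10.10).
- 25% dropout (Protocol 4.10.8: "Assuming a 25% dropout rate, two-sided testing at an overall 0.05 level").
- Optional entry to Period B (Protocol 3.2.1: "Continuation into Study Period B is optional").

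**Assumptions, because the documents give no figure**
- Constant event rates of 0.04, 0.08, 0.12 and 0.20 per year.
- 80% entry in the scenario with optional entry.
- Four binary strata split 50/50/25/10%.

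**Method.** Untreated time is U(ψ) = T_off + exp(ψ) × T_on. The estimate ψ̂ solves log-rank Z(ψ) = 0. Placebo times are set to U(ψ̂), crenezumab times are left as observed, and an ordinary log-rank is run. With A the switch time and C the censoring time, three re-censoring rules were tried:
- none;
- switch-time, min(C, A + exp(ψ)(C − A));
- full, min(C, exp(ψ)C).

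**Rejection under the null at nominal 5%** (8,000 replicates per rate, Monte Carlo SE about 0.3 points). Base case: universal entry, no dropout, unstratified.

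| Rate/yr | As-randomized | None | Switch-time | Full |
|---|---|---|---|---|
| 0.04 | 5.4% | 11.4% | 10.7% | 7.9% |
| 0.08 | 4.9% | 9.7% | 9.4% | 7.1% |
| 0.12 | 5.0% | 9.1% | 8.9% | 7.0% |
| 0.20 | 5.2% | 7.9% | 7.7% | 6.3% |

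With 25% dropout, 80% entry and the stratified test:

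| Rate/yr | As-randomized | None | Switch-time | Full |
|---|---|---|---|---|
| 0.04 | 5.0% | 8.2% | 7.8% | 6.3% |
| 0.08 | 5.0% | 7.5% | 7.2% | 5.9% |
| 0.12 | 5.3% | 6.9% | 6.8% | 5.7% |
| 0.20 | 5.2% | 6.4% | 6.3% | 6.1% |

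**Direction.** Rejections favouring crenezumab should be 2.5%. With no or switch-time re-censoring they are 3.9–5.5% in the base case and 3.2–3.8% in the second scenario. With full re-censoring they are 2.2–2.7% and 2.4–3.1%, so most of the excess falls against the drug.

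**Drivers at 0.08/yr** (none/switch-time/full; base 9.7/9.4/7.1%):
- strata only: 9.7/9.2/7.3%
- dropout only: 9.4/8.9/6.8%
- dropout and 80% entry: 8.5/8.3/6.9%

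**Coverage of the nominal 95% HR interval at 0.08/yr** (2,000 datasets, 200 resamples each, SE about 0.5 points; none/switch-time/full):

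| Interval | True HR 1 | True HR 0.70 |
|---|---|---|
| Planned Cox | 90.2/90.5/93.0% | 91.5/91.5/93.5% |
| Test-based from as-randomized statistic | 95.3/95.3/95.3% | 95.1/94.4/92.5% |
| Bootstrap SE, factor re-estimated | 95.4/95.3/96.7% | 95.3/95.0/97.5% |
| Bootstrap percentile | 93.9/93.9/94.0% | 94.2/94.2/95.9% |

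**Second simulation, separate code** (4,000 replicates in the main scenarios; 20–80% of participants with events; with and without 25% dropout). The planned test rejected in 7.5–11.2% without and 6.5–7.3% with re-censoring under a constant hazard, and in 8.3–12.4% and 6.8–8.3% under a rising hazard. The as-randomized test rejected in 4.5–5.6%. In smaller checks:
- 70% entry gave 6.9–8.7% without and 5.8–6.0% with re-censoring.
- An iterative Weibull estimate of the factor gave 11.0% (800 replicates).
- 3.5 years after the switch gave 11.4–14.3% without and 8.4–12.2% with re-censoring.

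**The case against.** The strongest reply is that little rests on these p-values. The alpha-controlled tests of the same two endpoints (SAP 5.4) are ordinary stratified log-rank tests on Period A data, with no switching and no estimated factor. The RPSFT tests carry no alpha and no decision rule, and they are exploratory if the study is terminated on Period A. All of this stands and limits the consequence. It does not make a nominal 95% interval that covers about 90% acceptable if Period B is extended.

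A second reply is that the 11.4% needs the lowest assumed event rate, universal entry, no dropout, no strata and no re-censoring. That also stands: 5.7–8.2% is closer to the documents' conditions. Dropout alone is a weak driver, and Period B entry, event rate and re-censoring matter more. With full re-censoring, false claims of benefit stay close to nominal.

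A third is that RPSFT keeps the intention-to-treat p-value by construction. That is true of g-estimation, but the SAP places the log-rank after the adjustment. If the as-randomized p-value is meant, one sentence would settle it.

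The simulations are also unconditional. They do not model the sponsor's decision to continue after Period A, and they include no open-label data.

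**Conclusion.** The concern holds. Followed as written, SAP 5.10.1.2 gives p-values that are too small and HR intervals that are too narrow. Null rejection is about 6–11% across the rates and re-censoring rules in the main simulation, and about 6–8% with dropout, optional entry and strata. Planned interval coverage at 0.08/yr is 90.2–93.0% under the null and 91.5–93.5% at a true HR of 0.70. Whether the excess favours crenezumab depends on the unstated re-censoring rule.

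The exact size rests on assumed event rates, hazard shape and Period B entry, so confidence in it is medium. The direction held at every rate tried and in both simulations. Family-wise error is not breached. This should be fixed before the Period B analysis, but it does not threaten the Period A conclusions.

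**What to change.** 1. Take the p-value from the as-randomized stratified log-rank over Periods A and B.
2. State the re-censoring rule.
3. Report the acceleration factor with the CI from the same log-rank inversion that estimates it. That CI excludes 1 exactly when the as-randomized test is significant, and it covered 94.7–95.1% at HR 0.70.
4. For the adjusted HR, use log HR ± 1.96 × a bootstrap SE, re-estimating the factor in every resample. A test-based interval from the as-randomized statistic is an alternative if re-censoring is absent or switch-time only; with full re-censoring it under-covers (92.5% at HR 0.70). The bootstrap-SE interval is somewhat conservative with full re-censoring, and the percentile bootstrap slightly under-covers near HR 1 (about 94%).
5. Note in the SAP that a bootstrap interval can exclude 1 when the as-randomized p-value is not significant (1.8% of null datasets for the percentile version).

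The cost is SAP wording and a short program, with no new data. With no or switch-time re-censoring, the HR interval widens by about 17–18% on the log scale (mean width 0.87 to 1.02–1.03 at 0.08/yr under the null). The as-randomized p-value includes follow-up with both arms on crenezumab, so it will reach significance less often than the planned one.

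A separate minor clarification: state that time to a non-zero CDR is analysed in carriers whose baseline global CDR is 0.
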